5.3 Ancillary Data

Additional ancillary data to be collected and evaluated include:

- Balloon slippage
- Catheter performance questionnaire
- All adverse events, categorized per CEC adjudication
- Device deficiencies

- Protocol deviations
- Screen failure tracking

6.0 STUDY DESIGN

6.1 Overall Design

The investigation is a prospective, multi-center, single arm clinical study. Subjects will be followed through hospital discharge. The study design is similar to comparable devices in the population under study; in particular, the Scoreflex NC is currently being evaluated in an ongoing clinical study to support regulatory market applications.

After screening for initial inclusion and exclusion criteria, eligible subjects will be asked to participate in the study by signing a consent form. Following consent, subjects will undergo a baseline visit where additional eligibility criteria will be assessed. An angiogram will be completed to assess for angiographic eligibility. If any angiographic inclusion criteria are not met or any of the angiographic exclusion criteria are met, the patient will not be enrolled. If all angiographic inclusion criteria are met and none of the angiographic exclusion criteria are met, subjects may undergo treatment with the Lacrosse NSE ALPHA. If a non-target lesion is identified, it must be treated successfully prior to target lesion treatment. Once treatment of the target lesion(s) has been attempted, the subject will be considered enrolled in the study.

Subjects will be followed through hospital discharge.

6.2 Number of Sites & Subjects

The study will be conducted in up to 15 investigational sites in the U.S. This study will enroll and treat 200 subjects, including a minimum of 30 subjects with ISR. Enrollment will continue until both the overall target of 200 and the ISR cohort of 30 have been obtained. More specifically, enrollment of non-ISR subjects will be capped at 170 such that if and when this maximum has been achieved without 30 ISR subjects, only ISR subjects will be permitted to be enrolled until the minimum of 30 has been reached, for a total of 200 subjects. Detailed sample size calculations and statistical methods are contained in **Section 8.6** and in the statistical analysis plan. No single site will enroll more than 20% of the total enrollment.

6.3 Study Population

The population for this study is subjects with stenotic coronary artery disease who are suitable candidates for PTCA.

The study will be conducted in adult subjects (18 years or older) and does not include any age, gender, or racial and ethnic origin restrictions. Women who have known pregnancy or who are nursing are excluded because of the risks of radiation exposure that occurs during the PTCA procedure and the medications (e.g., blood thinners) that may be needed.

Medicare-eligible patients (age 65 and up) will be included in the subject population. Two recent articles support that a large number of subjects undergoing PCI are in this age group.

- A publication (Kandzari) from the Scoreflex NC trial (IDE G180168, NCT NCT03763747) reported mean age of 67.3 [SD 8.98] years. The product and intended patient population in the Scoreflex NC trial are substantially similar to those in the EXPANSE-PTCA study; these data indicate that a considerable fraction – likely a majority -- of subjects in the current study population will be Medicare-eligible.
- A retrospective cohort study (Alkhouri) used a national inpatient claims-based database to identify patients undergoing PCI or CABG from 2003 to 2016 and reported demographic characteristics into 3 distinct time frames (2003-2007, 2008-2012, and 2013-2016). Of the 1,877,560 patients that underwent PCI in the most recent time frame (2013-2016), 43.1% were aged 65-85, with an additional 4.8% were greater than 85 years. In the same cohort, 60.9% of patients were Medicare or Medicaid patients.

Based on these two publications, and the intended population for this study, study enrollment is anticipated to include a substantial proportion of Medicare-eligible subjects and results are therefore expected to be generalizable for Medicare beneficiaries due to age, disability, or other eligibility status.

6.4 Study Duration

Enrollment is expected to take approximately 12 months. Each subject will actively participate in the study through hospital discharge. The overall study duration, from subject enrollment through final report, is expected to be approximately 18 – 24 months.

6.5 Subject Eligibility Criteria

6.5.1 Inclusion Criteria

Subjects must meet all the following inclusion criteria:

General inclusion criteria

1. Age 18 years or older.
2. Willing to provide written informed consent and written Health Insurance Portability and Accountability Act (HIPAA) authorization prior to initiation of study-related procedures.
3. Agree to not participate in any other clinical study, during hospitalization for the index procedure, that would interfere with the endpoints of this study.
4. Clinical evidence of ischemic heart disease, stable/unstable angina, or silent ischemia.
5. Acceptable candidate for PCI and emergency coronary artery bypass grafting (CABG) and is planned for possible PTCA and/or stent placement.

Angiographic inclusion criteria

6. *De novo* or restenotic lesion(s) in native coronary arteries, including in-stent restenosis.
7. A maximum of two lesions, including at least one target lesion, in single or double vessel coronary artery disease.
 - a. If two target lesions are defined, then no non-target lesions can be treated.

- b. If a single target lesion is defined, then a single non-target lesion may be treated, but if so, it must be located in a different coronary artery from the target lesion.
- 8. Target lesion(s) must have a reference vessel diameter (RVD) between 2.0 mm and 4.0 mm by visual estimation.
- 9. Target lesion(s) must have a diameter stenosis of (a) $\geq 70\%$ by visual estimation or (b) $>50\%$ by visual estimation and a fractional flow reserve (FFR) of <0.80 or resting full-cycle ratio (RFR) or instantaneous wave-free ratio (iFR) <0.9 .
- 10. Treatment of non-target lesion, if any, must be completed prior to treatment of target lesion; must not, in the opinion of the investigator, impact the conduct or completion of the index procedure; and must be deemed a clinical angiographic success as visually assessed by the investigator.

6.5.2 Exclusion Criteria

Subjects must not meet any of the following exclusion criteria:

General exclusion criteria

- 1. Known hypersensitivity or contraindication to aspirin, heparin, bivalirudin, anti-platelet medications, a clopidogrel non-responder, or sensitivity to contrast media that cannot be adequately pre-medicated or replaced with a clinically suitable alternative.
- 2. Known diagnosis of type I myocardial infarction (resulting from primary reduction of flow from a culprit lesion likely to have a thrombotic component) within 7 days prior to the index procedure.
- 3. Known pregnancy or is nursing. Women of child-bearing potential should have a documented negative pregnancy test within 7 days prior to index procedure.
- 4. Planned target lesion treatment with atherectomy (rotational, orbital or laser), cutting balloon, thrombectomy, lithotripsy or an unapproved device during the index procedure.
- 5. Serum creatinine >2.0 mg/dl within 7 days prior to the index procedure.
- 6. Cerebrovascular accident within 6 months prior to the index procedure.
- 7. Active peptic ulcer or active gastrointestinal bleeding within 6 months prior to the index procedure.
- 8. Left ventricular ejection fraction (LVEF) $<30\%$ based on most recent measurement within a year of the index procedure (if LVEF is not available in the medical records, it may be obtained at the time of the index procedure, prior to enrollment).
- 9. Target lesion located within a bypass graft (venous or arterial) or graft anastomosis.
- 10. Previous percutaneous intervention, within 9 months before the study procedure, on lesions in a target vessel (including side branches) that are located within 10 mm from the current target lesion(s).
- 11. Target lesion(s) with complete total occlusion (CTO) defined as the complete obstruction of a native coronary artery, exhibiting TIMI 0 or TIMI 1 flow, with an occlusion duration of at least 3 months.

12. Unstable hemodynamics or shock.
13. Other medical condition which might, in the opinion of the investigator, put the patient at risk or confound the results of the study.

Angiographic exclusion criteria

14. Target lesion(s) longer than 32 mm by visual estimation.
15. Extreme angulation (90° or greater) within 5 mm of the target lesion.
16. Target lesion(s) demonstrating flow limiting dissection (NHLBI Grade C or higher)
17. Unprotected left main coronary artery disease (>50% diameter stenosis).
18. Coronary artery spasm of the target vessel in the absence of a significant stenosis.
19. Target lesion(s) with angiographic presence of probable or definite thrombus.
20. Target lesion(s) involves a bifurcation requiring treatment with more than one stent or pre-dilatation of a side branch >2.0 mm in diameter.
21. Target lesion(s) located in bifurcation beyond stent struts.
22. Target lesion(s) located distal to an implanted stent.
23. Target lesion(s) with stent damage.
24. Non-target lesion that meets any of the following criteria:
 - Located within a bypass graft (venous or arterial)
 - Located in an unprotected left main coronary artery
 - A CTO
 - Involves a bifurcation

7.0 STUDY METHODOLOGY

Study evaluations and data collection points are described below and visually represented in **Figure 3** and in **Table 2** below. To avoid missing data in the study, subjects should be followed for all regularly scheduled visits for safety and effectiveness assessments. Any reason for withdrawal from the study should be documented as described later in the protocol. See **Section 13.0** for definitions of adverse event and endpoint-related terms used in this section.

Study procedures should be followed carefully as they have been designed to address foreseeable factors that could compromise the outcome of the study or interpretation of results. This includes inclusion/exclusion criteria designed to address potential subject-related factors, treatment procedures to address foreseeable factors related to concomitant medication and/or medical procedures, and follow-up procedures to permit the demonstration of clinical performance and safety over a sufficient period of time.

The remainder of this page is intentionally blank

Figure 3: Study Flow Diagram

[figure not shown]

Table 2: Evaluations & Data Collection Points

Evaluations	Screening / Baseline	Treatment Procedure ¹	Post-Procedure/ Discharge
Subject informed consent	X		
Inclusion/exclusion assessment - general	X		
Demographics & medical/surgical history ²	X		
Pregnancy test ^{3, 4}	X		
Serum creatinine ⁴	X		
Coronary angiography (send to core lab) ⁵		X	
Inclusion/exclusion assessment – angio ⁵		X	
PCI procedure		X	
Device performance assessment		X	
Device deficiency assessment		X	
Adverse event assessment ⁶		X	X
Catheter performance questionnaire			X

¹ Within 30 days of screening / baseline
² Medical history collected within 14 days of the index procedure
³ If female with child-bearing potential
⁴ Completed within 7 days of the index procedure
⁵ Angiography occurs in cath lab, prior to treatment, to determine enrollment eligibility
⁶ Adverse event assessment begins at the time of enrollment

7.1 Screening

Screening is defined as the process of reviewing a patient's medical records against the study eligibility criteria to determine if the patient is potentially eligible to enroll in the study. It is expected that the medical records will contain adequate information to determine if a patient meets most of these criteria. Eligible patients are those potentially requiring PCI for stenotic coronary arteries.

If the investigator (or designee) determines the patient meets all clinical inclusion and exclusion criteria (except criteria verified by blood testing after consent), they can be consented for study participation, after which all remaining non-angiographic eligibility criteria will be verified prior to the procedure.

Final study eligibility can only be assessed in the cath lab using angiographic inclusion and exclusion assessments. During the pre-intervention angiography, some consented subjects may be determined ineligible for study enrollment; these subjects will be categorized as screen failures. Sites will be required to maintain a screen failure log, that contains rationale for subjects who became screen failures after consent.

7.2 Informed Consent Process

Prior to enrolling patients in this study, the site will be required to have an Institutional Review Board (IRB) approved informed consent form (ICF). The clinical research organization (CRO) must review any modifications made to the sponsor's template ICF prior to IRB submission.

Written informed consent will be obtained from the patient (or the patient's legal representative) prior to participation in the study. The investigator (or authorized designee) will explain the nature of the planned treatment and objectives of the study to the patient, along with any costs to the patient, payments for participation, and types of insurance provided (if applicable). The investigator will allow adequate time for the patient to read and review the consent form and to ask questions. When the investigator has reasonable assurance that the patient (or legal representative) has an acceptable level of comprehension and the patient (or legal representative) voluntarily agrees to participate, the patient (or legal representative) and the investigator (or authorized designee) will sign and date the IRB-approved ICF.

The site will retain the original signed ICF in the subject's study records and will provide a copy of the signed ICF to the subject. The site will document the consent process (e.g., that the subject was consented, the date on which the consent was obtained, and that a copy of the signed ICF was given to the subject) in the subject's medical records.

Subjects will be informed of any new information that may make him/her change their mind about staying in the study. Subjects may be asked to sign a new ICF if this occurs.

7.2.1 Vulnerable Population

The sponsor is not anticipating enrollment of a vulnerable patient population (ref. ISO 14155:2020 sections 5.7 and A.6.3).

7.2.2 Point of Enrollment & Numbering of Study Subjects

A patient will be considered enrolled as a study subject once an investigational Lacrosse NSE ALPHA catheter has entered the guiding catheter ("attempt to treat").

Note: Successful treatment of any non-target lesion is required prior to enrollment.

As soon as possible after a subject is enrolled, the site will notify the CRO, preferably by an entry in the electronic data capture (EDC) database or via email notification. The database will assign the lowest available patient enrollment ID, progressing sequentially for each enrolled subject (e.g., 0001, 0002, 0003). Subject ID assignment will follow Infraredx procedure CS0110.

7.3 Baseline

The following standard of care evaluations and assessments will be performed at baseline and documented on the relevant electronic case report forms (eCRFs):

- Demographics
- Medical and surgical history obtained within 14 days of the procedure (including key comorbidities and prior coronary interventions (e.g., PCI, CABG))

- Pregnancy test (if female with childbearing potential), per standard of care for PCI (within 7 days of procedure)
- Serum creatinine (within 7 days of procedure)

After the baseline evaluations, the inclusion and exclusion criteria should be re-reviewed to ensure that the subject continues to be eligible for the study.

7.4 Pre-PCI Procedure Angiogram

The site will follow standard catheterization procedures and angiographic procedures recommended by the core laboratory. A pre-procedure angiogram of the target lesion will be completed per the Angiographic Core Laboratory Guidelines prior to any interventions. Assessment of angiographic eligibility is based on a visual assessment of the pre-procedure angiogram by the investigator.

7.5 Treatment Procedure & Immediate Post-Procedure Assessment

The PCI procedure will be performed following these guidelines:

- A maximum of one non-target lesion, if identified, must be located in a different coronary artery from the target lesion and must be treated first and deemed a clinical angiographic success, as visually assessed by the physician. Study devices cannot be used on this non-target lesion.
- Target lesion will be treated using the Lacrosse NSE ALPHA following the device instructions for use.
- A target lesion composed of multiple focal lesions that can be covered with one stent will be considered as a single lesion.
- A separate Lacrosse NSE ALPHA study device must be used for treatment of each target lesion.

Additional procedures and interventions may be performed per standard of care at the discretion of the treating investigator (except those defined in the exclusion criteria).

Post-procedure angiographic imaging of the target lesion must be captured and performed per the instructions provided by the core laboratory and must be captured in the same precise manner as was used for the pre-procedure images. Angiographic images must be sent to the core lab following the instructions provided by the core laboratory.

Standard PCI procedural data will be collected on the eCRFs, such as:

- Vessel and lesion characteristics, including MLD and diameter stenosis (%)
- TIMI grade flow pre- and post-treatment
- Type and size of study devices used, including lot number
- Device performance assessment, including balloon slippage
- Procedural durations, including start/end times
- Air kerma (Gy) and total fluoroscopy time

- Adverse event assessment, including perforation and dissection classifications
- Device deficiency assessment

7.5.1 Post-procedure / Discharge

The following evaluations and assessments will be performed at 18-24 hours post-procedure or directly prior to discharge, whichever occurs first, and documented on the relevant eCRFs:

1. Catheter performance questionnaire
2. Adverse event assessment

After the subject is discharged, participation in the study is complete and the site will fill out the Study Completion eCRF. Subjects will continue to be followed by their physician per usual care.

7.6 Early Withdrawal / Premature Discontinuation of Subjects

Subjects may be withdrawn early from the study for several reasons including:

- Subject death
- Subject request for withdrawal (withdrawal of consent)
- Investigator decision, to be fully documented
- Adverse event

If a subject is discontinued from the study early, a Study Completion eCRF must be completed describing the reason for early discontinuation. If a subject chooses to withdraw from the study and also withdraws consent for disclosure of further information, no further evaluation(s) should be performed, and no additional data collected. The sponsor may retain and continue to use any data collected prior to the withdrawal of consent.

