$$H_0: r \leq PG$$

$$H_A: r > PG,$$

where r is the proportion of endpoint successes and PG is the performance goal of 87.7% = 0.877.

The hypotheses will be tested at a one-sided alpha level of 0.05 and endpoint success will be declared if the performance goal is met (i.e., if the null hypothesis above is rejected in favor of the alternative hypothesis). For primary analysis, this endpoint will be tested on all subjects with available data, with a worst-case sensitivity analysis also incorporated as noted below.

Among the 200 subjects intended for enrollment, a subgroup of at least 30 is intended to be cases of in-stent restenosis. The value of 30 is a commonly used benchmark and is chosen to provide a reasonable sample size to characterize outcomes in this subgroup (Hogg, 2005), as well as a feasible target from a clinical perspective. The ISR subgroup is not intended for formal statistical hypothesis testing independent of the entire study cohort as the study is powered for the full 200 subjects planned for enrollment; hence no decision rule specific to ISR cases is defined. However, key outcomes, including the primary endpoint, will be compared between the *de novo* and ISR cohorts to assess any statistically significant differences. This testing will be performed on an exploratory basis and hence no alpha allocation for multiplicity is necessary, nor will overall analytical conclusions be driven by the number of ISR cases.

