11.2 Adverse Event Collection & Documentation

Collection of adverse events will start when subjects are enrolled and will be assessed and reported throughout the study. Investigators must obtain all information available to determine the relatedness and outcome of the adverse event and to assess whether it meets the criteria for classification as an unanticipated adverse device effect (UADE) requiring immediate notification. All adverse events will be followed until resolution or investigator determination that the subject's condition is stable.

All reported adverse events will be documented on the Adverse Event eCRF. Copies of de-identified source documentation that contain significant information related to the event, such as progress notes, consultations, nurse's notes, operative reports and subject summaries may be requested by the sponsor, CRO, CEC, and/or angiographic core lab as needed for evaluation and adjudication.

The following are not considered adverse events for this study:

- Any condition that is recorded as pre-existing on the Baseline eCRF, unless there is a worsening of that condition in terms of nature, severity, or degree of incidence.
- Any normal expected symptoms associated with PCI unless the event involves a clinically significant change in severity or duration of symptoms or requires clinical intervention that is different from ordinary postoperative care. The following are examples of the normal responses to all PCI procedures and are not considered adverse events:
 - Transient arterial spasm resolving spontaneously OR with medication only

- Transient sinus bradycardia with heart rate ≤50 bpm, with no hemodynamic impact, and resolving spontaneously (prophylactic placement and automatic activation of a cardiac pacer during this transient period does not constitute an intervention)
- Minor discomfort or bruise at the arterial access place
- Small amount of bleeding at point of arterial access that does not result in a hematoma >5 cm, need for transfusion, or hemodynamic compromise
- Side effects of standard-of-care medications

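### Withdrawal for an adverse event is allowed with no statement that endpoint observation continues to discharge, and the primary test can omit a subject whose final TIMI is missing because of a complication

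*Protocol*

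**What the plan says.** **Withdrawal.** Protocol 7.6 opens with "Subjects may be withdrawn early from the study for several reasons including" and lists death, subject request, investigator decision and "Adverse event". It requires a Study Completion eCRF giving the reason. The only case in which it expressly stops data collection is a subject who withdraws and also "withdraws consent for disclosure of further information, no further evaluation(s) should be performed, and no additional data collected".

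**End of participation.** Protocol 7.5.1: "After the subject is discharged, participation in the study is complete and the site will fill out the Study Completion eCRF". It adds: "Subjects will continue to be followed by their physician per usual care". No exception is made for an unresolved event.

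**Adverse-event follow-up.** Protocol 11.2: "All adverse events will be followed until resolution or investigator determination that the subject's condition is stable". Protocol 7.0 sets the general aim: "To avoid missing data in the study, subjects should be followed for all regularly scheduled visits for safety and effectiveness assessments".

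**Endpoints.** MACE, stent thrombosis and clinically significant arrhythmia run through hospital discharge (Protocol 5.2, SAP 6.2). The primary endpoint requires, among other components, TIMI 3 at the end of the procedure as read by the core laboratory (Protocol 5.1, SAP 6.1).

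**Analysis.** Under Protocol 8.3 and SAP 9.1, "this endpoint will be tested on all subjects with available data". The same sentence adds a worst-case sensitivity analysis, for which Protocol 8.8 and SAP 7.4 give missing-as-failure as the example, for the primary endpoint only. SAP 8.1 tabulates non-completers by reason and says nothing about how they count in the safety endpoints.

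**The concern.** A subject withdrawn for an adverse event is, by selection, one with a complication and so plausibly at higher risk of a further in-hospital event. If a site reads withdrawal as the end of observation, the loss is caused by the kind of outcome being counted. The bias then runs one way, towards lower MACE, stent thrombosis and arrhythmia proportions. No sensitivity analysis is planned for those endpoints.

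A second gap is at discharge. One section closes the subject and another keeps the event open, so two sites could handle the same unresolved event differently and leave its outcome unrecorded in one of them.

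A third is in the primary analysis and does not depend on withdrawal. Death or emergency surgery during the procedure may mean that no final film exists. If nothing else has failed on record, a very poor procedural result is handled as missing data and left out of the test that decides success.

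**Working it through.** **1. Safety endpoints: the provisions side by side**

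| Situation | 7.6 | 7.5.1 | 11.2 | Loses through-discharge endpoint events? |
|---|---|---|---|---|
| Withdrawn for an adverse event before discharge | Allowed; form required; silent on further observation | Not addressed | Follow the event to resolution or stability | Possibly, if the site stops observing |
| Event open at discharge | Not addressed | Participation complete | Follow the event to resolution or stability | No; only the event's outcome |
| Consent for disclosure withdrawn | Data collection stops | Not addressed | Overridden | Unavoidable |

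Section 11.2 governs follow-up of the event already reported. It does not clearly require watching a withdrawn subject for a new endpoint event, so it only partly fills the silence in 7.6.

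Size: the documents give no MACE rate and no withdrawal rate. With 200 subjects kept in the denominator, each unseen MACE lowers the proportion by 1/200 = 0.5 percentage points. If 1 to 5 such events were missed (an assumption), the understatement would be 0.5 to 2.5 points. As a further assumed example, 4 true events give 4/200 = 2.0% (exact 95% CI 0.5% to 5.0%). If two are unseen and those subjects also leave the denominator, the report is 2/198 = 1.0% (0.1% to 3.6%). Nothing in the documents says that withdrawn subjects leave the denominator; with all retained it is 2/200 = 1.0%.

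**2. Primary endpoint: the plan's own figures first**

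Inputs (Protocol 8.3 and 8.6; SAP 9.1 and 10): null 0.877, assumed rate 0.935, N = 200, one-sided alpha 0.05, exact binomial test. The p-value for r successes in n is P(X ≥ r), with X ~ Bin(n, 0.877).

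- N = 200: the smallest r with p ≤ 0.05 is 184 (p = 0.0351). Power = P(X ≥ 184) with X ~ Bin(200, 0.935) = 84.3%. The stated 84% reproduces.
- 5% missing, N = 190: smallest r = 175 (p = 0.0354), power 82.5%. The stated figure of above 80% reproduces.

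**3. Primary endpoint: leaving out complication cases with no final TIMI**

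| Successes | Scored as non-success | Left out |
|---|---|---|
| 183 | 183/200 = 91.5%, p = 0.058, fails | one omitted: 183/199 = 92.0%, p = 0.037, passes |
| 182 | 182/200 = 91.0%, p = 0.091, fails | two omitted: 182/198 = 91.9%, p = 0.039, passes |

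At n = 199 the smallest passing count is 183, so one omission does not rescue 182.

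A reversal needs the final count to lie at the edge. If the true rate is 0.935, exactly 183 successes of 200 has probability about 5.5% and exactly 182 about 3.9%, before requiring that one or two non-successes be of this kind.

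**4. Can such a subject exist under the definition?**

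All components must be met, so any recorded failure (delivery, inflation, deflation, withdrawal of the balloon, device-related perforation, dissection of grade C or higher, reduced TIMI) already settles the subject as a non-success. The gap is left for a subject with successful balloon use, no qualifying perforation or dissection, and no final film for the core laboratory to read. Neither document says how that subject is scored.

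**The case against.** The strongest reply is that the plan already covers most of this. Section 7.6 expressly stops data collection only when consent for disclosure is withdrawn, so after an adverse-event withdrawal 11.2 can be read as still in force. Death is already a MACE component, and 11.2 asks for death records or a written account. Protocol 12.6 requires full source verification of endpoint and adverse-event data and a search for unreported events. Missing primary data are tested by the worst-case analysis, which in the examples above would report 183/200 and 182/200 openly. Nor does withdrawal always come after all study treatment: a subject with two target lesions may have an event before the second is treated.

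Much of that stands. A reader might infer that 7.6 orders observation to stop; it does not, it is silent. A reader might infer that closing subjects at discharge biases MACE, stent thrombosis or arrhythmia; it cannot, because those endpoints end at discharge. A reader might infer that withdrawal under 7.6 changes the primary result; it does not once the procedure is over, because the endpoint is settled by then. The missing-film point is a separate matter of scoring.

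What does not stand is that nothing needs changing. Silence on observation leaves the choice to each site. Monitoring checks what is in the source and does not require a withdrawn subject to be observed. The worst-case analysis does not decide success and does not extend to the safety endpoints.

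**Conclusion.** The point holds as three limited gaps.

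- **Observation after withdrawal.** The protocol does not say that a subject withdrawn for an adverse event is still observed for endpoints to discharge. Any bias would understate in-hospital safety events. Its size is unknown: 0.5 percentage points per missed subject with MACE, with the number missed an assumption.
- **Events open at discharge.** Sections 7.5.1 and 11.2 conflict. The consequence is confined to adverse-event outcomes.
- **Complication-caused missing final TIMI.** Such a subject can drop out of the deciding test. The declared result changes only close to 184/200 (183/200, p=0.058, against 183/199, p=0.037), and only if the omitted subject failed no other component. The planned sensitivity analysis would reveal it without altering the decision.

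The power statement is sound, and the plan's figures reproduce. The changes are worth making because they are specific and cheap, not because a distorted result is likely.

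**What to change.** 1. **Protocol 7.6.** State that a subject withdrawn for an adverse event or by investigator decision is still observed for endpoints through discharge unless consent is withdrawn, and that death is recorded as an outcome.
2. **Protocol 7.5.1, 7.6 and 11.2.** Reconcile these so that they give one rule for an event open at withdrawal or at discharge, and align the Study Completion eCRF instruction with it.
3. **Protocol 8.3 and 8.8; SAP 7.4 and 9.1.** Score a final TIMI that is missing because of death, emergency surgery or another procedural complication as non-success in the primary analysis. Leave other missing data as planned, with the worst-case analysis retained.

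The cost is protocol and SAP wording, an eCRF instruction, and a little extra follow-up of open events, which 11.2 already calls for. The observed success rate may be marginally lower.
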